Dosing: FPA150 will be administered as a single agent in a 60-minute (± 5 minutes) IV infusion Q3W, on Day 1 of each 21-day cycle. The dose of FPA150 will be based on body weight at Cycle 1 Day 1 (C1D1). After Cycle 1, the FPA150 dose will be recalculated at each infusion visit only if the patient's weight has changed $> 10\%$ from Cycle 1, Day 1. There is no pre-specified maximum number of doses of FPA150 for patients receiving monotherapy.

Patients may continue receiving FPA150 monotherapy according to their study specified cohort/dose until Investigator-assessed clinical progressive disease, unacceptable toxicity, or the patient meets any of the other protocol-specified withdrawal criteria (refer to Section 7).

For combination cohorts, pembrolizumab will be administered at a dose of 200 mg IV over 30 minutes (\pm 5 minutes) starting on C1D1 after the completion of FPA150 infusion. Dosing for combination cohorts will be repeated on Day 1 of each 21-day cycle. Patients in the combination cohort may receive one or both drugs in combination according to their study specified cohort/dose until Investigator-assessed clinical progressive disease, unacceptable toxicity, or the patient meets any of the other protocol-specified withdrawal criteria (refer to Section 7). Patients treated with the combination would be able to receive pembrolizumab treatment for up to 24 months. If one of the two drugs has to be discontinued, patients may continue to receive the other drug alone.

Treatment beyond disease progression may be allowed in patients with progressive disease according to Response Evaluation Criteria in Solid Tumors version 1.1 (RECIST v1.1) if the benefit/risk assessment favors continued administration of study treatment (eg, if patients are continuing to experience clinical benefit as assessed by the Investigator, and tolerating treatment).

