4.1.2.2.2 FPA150 Combined with Pembrolizumab (Safety Lead-in)

Additional DLT Considerations for the Combination of FPA150 and Pembrolizumab

Because pembrolizumab is a known immune checkpoint inhibitor and one of the proposed mechanisms of action of FPA150 is immune checkpoint blockade, immune-related adverse events (irAEs) are anticipated with this combination. An irAE is defined as a clinically significant AE that is associated with study drug exposure, of unknown etiology, and is consistent with an immune-mediated mechanism. Based on that background, the first occurrence of the following irAEs will not be considered a DLT because they are expected with immune therapy:

- Grade 3 tumor flare (defined as local pain, irritation, or rash localized at sites of known or suspected tumor)
- Grade 3 rash
- Grade 3 immune-related adverse event (irAE) that resolved to a Grade 1 or less within 14 days
- Transient (resolving within 6 hours of onset) Grade 3 infusion-related AE

A second occurrence of these events (except Grade 3 tumor flare) either in the same or different patient during the DLT period will be considered a DLT

4.1.2.3 Dose-Limiting Toxicity Evaluation and Dose Escalation (FPA150 Monotherapy and Combination Safety Lead-in)

The DLT evaluation interval begins on the first day of treatment upon start of infusion and continues for 21 days. In Phase 1a Dose Escalation, patients' second dose must be at least 21 days after the first dose.

Review of safety, PK and pharmacodynamic profiles may inform decisions to add cohorts with alternative dose levels or dose regimens (eg, different dosing frequency, higher dose levels) in order to reach an optimal target exposure.

All dose escalation decisions will be based on the assessment of DLTs and overall safety and tolerability, and will be made after the last patient enrolled in each cohort has completed the first treatment cycle (ie, 21 days). Dose escalation decisions will be agreed upon by the CRC as outlined in Section [4.1.1](#).

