Patients who receive at least one dose of study drug during the 21-day evaluation interval, or patients who discontinue study treatment for drug-related AEs before the DLT evaluation interval is complete, will be considered evaluable for DLT determination. Patients who discontinue study treatment for reasons other than drug-related AEs before the DLT evaluation interval is complete may be replaced. In consultation with Investigators, the Sponsor may open cohorts at dose levels between the dose levels proposed in the protocol.

For monotherapy dose escalation an accelerated titration design enrolling at least 1 patient at each dose level is planned for dose levels 0.01, 0.03, 0.1, and 0.3 mg/kg. Dose escalation to the next dose level may proceed after at least 1 patient completes the 21-day evaluation interval. If a single patient experiences a DLT or at least 2 patients experience moderate AEs (at any dose level) during the 21-day evaluation interval, additional patients will be enrolled at the current dose level and standard 3+3 dose escalation criteria will apply for that cohort as well as all subsequent dosing cohorts. Moderate AEs are defined as \geq Grade 2 AEs regardless of attribution (except for those events clearly due to the underlying disease or extraneous causes). Grade 2 laboratory values will not be considered as moderate AEs for this purpose unless accompanied by clinical sequelae.

The algorithm outlined in Table 5 will be used for all standard 3+3 dose escalation decisions in Phase 1a monotherapy. If not already applied at a lower dose level for the reasons stated above, escalation for dose levels \geq 1 mg/kg will follow standard 3+3 dose escalation criteria.

Table 5: Phase 1a Algorithm for FPA150 Monotherapy Dose-Escalation Decisions

Number of Patients with DLT at a Given Dose Level	Dose Escalation Decision Rule
0/3	Enroll 3 patients at next dose level (next/higher cohort)
1/3	Enroll 3 additional patients at current dose level (current cohort)
$\geq 2/3$	Stop enrollment. Enter 3 more patients at the previous dose level (previous/lower cohort), if only 3 were previously entered, or at an intermediate dose level
1/6	Enroll 3 patients at next dose level (next/higher cohort)
$\geq 2/6$	Stop enrollment. Enter 3 more patients at the lower dose level (previous/lower cohort), if only 3 were previously entered, or at an intermediate dose level

Abbreviations: DLT = dose-limiting toxicity.

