6.4.4 Dose Modification Criteria for FPA150

Dose reductions for FPA150 may be permitted for patients on treatment beyond the DLT Period and can be assessed using local laboratories. If a patient requires a dose reduction of FPA150 during the DLT period, they will be considered to have a DLT and be permanently discontinued from FPA150. Dose reductions for FPA150-related AEs should follow the guidelines outlined in [Table 10](#). The treating physician may choose to interrupt or discontinue FPA150 at any time outside of these guidelines if they believe it is necessary to ensure patient safety. It is recommended that the treating physician discuss the proposed dosing modification with the FivePrime medical monitor prior to making the change. Patients may resume FPA150 if the event returns to baseline or \leq Grade 1 in accordance with the guidelines outlined in [Table 10](#). Any variations from these guidelines must be discussed with the FivePrime Medical Monitor prior to dosing and must take into consideration the overall benefit and risks for the patient of continued participation in the study.

Table 10: Dose Modification Guidelines for FPA150 (Non-infusion Toxicity)

FPA150-related Toxicity Grade	Dose Schedule	New FPA150 Dose
Grade 1 or 2	No delay or missed dose required	100% of dose
Grade 3 (first occurrence)	Delay or miss dose until recovery to baseline or Grade 1	If recovery to baseline or Grade 1 within 28 days, may resume at 100% of starting dose or 1 dose lower ^a
Grade 3 (second occurrence)	Delay or miss dose until recovery to baseline or Grade 1	If recovery to baseline or Grade 1 within 28 days, may resume at 1 level lower ^a than previous dose or discontinue
Grade 3 (third occurrence) Grade 3 which does not recover to baseline or Grade 1 within 28 days Any Grade 4	Permanently Discontinue	N/A

^a Eg, 1 dose level lower for patients treated at 20 mg/kg is 10 mg/kg; 1 dose level lower for patients treated at 10 mg/kg is 3 mg/kg; 1 dose level lower for patients treated at 3 mg/kg is 1 mg/kg.

There is a \pm 3-day window for the first 3 scheduled FPA150 dosing visits. The first dose of each cycle is considered Day 1 of each cycle. Cycles will repeat every 21 days unless there is a treatment delay. Inpatient dose escalation will not be permitted above 1mg/kg except as detailed in [Section 6.4.2](#). Any patient whose dose of FPA150 is decreased cannot be subsequently increased.

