9.2 Populations for Analyses

The following analysis populations are defined for the study:

- Safety Population—all patients who have received any portion of at least one dose of FPA150.
- DLT-Evaluable Population—all patients enrolled into Phase 1 monotherapy and in combination with pembrolizumab who received at least two doses of FPA150 and completed Cycle 1 of treatment, or who experienced a DLT in Cycle 1.
- Pharmacokinetic Full Analysis Population: All patients who received at least one dose of FPA150 and had at least one FPA150 serum concentration result.
- Pharmacokinetic -Evaluable Population—all patients in the PK Full Analysis Population who had sufficient PK sample for the calculation of at least one PK parameter on at least one Study Day.
- Efficacy-Evaluable Population—all patients who met eligibility criteria, received at least one dose of FPA150, have measurable tumor lesions at baseline, and have at least one post-baseline disease assessment unless the death and clinical progressive disease occurred prior to the first post baseline disease assessment.

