3.1.3 DLT-Evaluable Analysis Set

The DLT-Evaluable Analysis Set includes all enrolled subjects in Phase 1 monotherapy and in combination with pembrolizumab who received at least 2 doses of FPA150, and completed Cycles 1 of treatment, or who experienced a DLT in Cycle 1.

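### The DLT-Evaluable set drops DLT-free patients who lack a second FPA150 dose, although the DLT window is one cycle and evaluability for dose decisions needs only one dose

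*Protocol*

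**What the plan says.** **Reporting set.** Protocol 9.2 admits patients "who received at least two doses of FPA150 and completed Cycle 1 of treatment, or who experienced a DLT in Cycle 1". SAP 3.1.3 carries the same condition: "who received at least 2 doses of FPA150, and completed Cycles 1 of treatment", or a DLT in Cycle 1. SAP 7.1.7 uses this set for the summary and listing of DLTs. DLT incidence is a Phase 1a primary endpoint (Protocol Table 1).

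**Dose-decision rule.** Under Protocol 4.1.2.3 the DLT interval runs 21 days from the start of the first infusion, and escalation decisions follow once the last patient in the cohort has completed that first cycle. Two groups are evaluable: "Patients who receive at least one dose of study drug during the 21-day evaluation interval" and "patients who discontinue study treatment for drug-related AEs before the DLT evaluation interval is complete, will be considered evaluable for DLT determination". The synopsis gives the same rule. Section 4.1.2.3 adds: "Patients who discontinue study treatment for reasons other than drug-related AEs before the DLT evaluation interval is complete may be replaced".

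**Timing of dose 2.** Dosing is every 21 days. In escalation the "second dose must be at least 21 days after the first dose" (4.1.2.3).

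**The concern.** In escalation the second dose cannot fall inside the DLT window, so the reporting set depends on something that happens after the observation period has closed. The condition is also one-sided. A patient with a Cycle 1 DLT enters whatever the number of doses, while a DLT-free patient must go on to Cycle 2.

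The patients lost are not a random subset. Some complete the window and then stop, for example for progression. Others stop inside it for a drug-related event below the DLT threshold, and they are informative about tolerability. Both kinds count under 4.1.2.3. The reported incidence of a primary endpoint therefore need not reproduce the counts on which the dose was cleared, and neither document reconciles the two rules.

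**Working it through.** The documents state no DLT rate or sample size that depends on this definition, so there is no plan figure to reproduce. The check compares the definitions and then illustrates the size.

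**1. Who counts where**

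| Patient | 4.1.2.3 | 9.2 / SAP 3.1.3 |
|---|---|---|
| DLT in Cycle 1 | counted | counted |
| Completes 21 days DLT-free, receives dose 2 | counted | counted |
| Completes 21 days DLT-free, no dose 2 | counted | dropped |
| Stops inside the window for a drug-related event that is not a DLT | counted | dropped |
| One dose, leaves early for an unrelated reason | evaluable if read literally, yet may be replaced | dropped |

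Rows 3 and 4 are the defect. Row 5 is different: the window was not observed, so leaving that patient out of the table is defensible.

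**2. Can row 3 occur in the combination lead-in?** The 21-day minimum before dose 2 is stated for dose escalation only. Section 6.4.4 allows a "3-day window for the first 3 scheduled FPA150 dosing visits", three days either side. Cycle 2 Day 1 is nominally Day 22, so a lead-in dose 2 could fall as early as Day 19. Completing Cycle 1 still does not guarantee dose 2. The synopsis says of the combination: "If one of the two drugs has to be discontinued, patients may continue to receive the other drug alone". A patient can therefore finish the window, stop FPA150 and stay on pembrolizumab.

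**3. Effect on the rate.** Let d be the DLTs, n the patients counted under 4.1.2.3, and k the DLT-free patients dropped. With no replacement, the reported rate is d/(n − k).

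- Cohort reported at six, d = 1: 1/6 = 16.7% becomes 1/5 = 20.0% (k = 1) or 1/4 = 25.0% (k = 2).
- Lead-in cohort filled to ten, d = 1: 1/10 = 10.0% becomes 1/9 = 11.1% or 1/8 = 12.5%.
- Cohort stopped at six, d = 2: 2/6 = 33.3% becomes 2/5 = 40.0%.
- d = 0: the rate stays 0% and only the denominator changes, for example 0/3 to 0/2.

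**4. How likely is k ≥ 1?** The documents do not give the share q of DLT-free patients who count under 4.1.2.3 but would be dropped. Taking q as an assumption and patients as independent, the chance that at least one of m DLT-free patients is dropped is 1 − (1 − q)^m.

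| q (assumed) | m = 5 (one DLT in six) | m = 9 (one DLT in ten) |
|---|---|---|
| 5% | 1 − 0.95^5 = 23% | 1 − 0.95^9 = 37% |
| 10% | 1 − 0.90^5 = 41% | 1 − 0.90^9 = 61% |
| 20% | 1 − 0.80^5 = 67% | 1 − 0.80^9 = 87% |

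**5. If patients are replaced.** Should 9.2 govern replacement under 7.3, and one DLT-free replacement be added, the table stays at 1/6 = 16.7% while the 4.1.2.3 rule counts 1/7 = 14.3%. The two still differ.

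**The case against.** The strongest objection is that little turns on this. Analyses are descriptive, and DLTs and study drug administration are both listed by subject, so a reader could rebuild either denominator. The bias is towards a higher reported rate, which is cautious for safety. Protocol 2.2.5.4 reports no DLTs in escalation at the cutoff. All of this stands and limits the size of the point. It does not remove a contradiction in the denominator of a primary endpoint.

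Several stronger readings are tempting, but the documents do not support them:

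- *The dose decisions, or the recommended dose, are compromised.* Decisions follow 4.1.2.3, not 9.2. The detailed process is in the CRC Charter, which is not among the documents.
- *A lead-in cohort at 1/6 is final.* Protocol Table 6 sends it on to as many as ten patients. At ten, the shift is about one to two and a half percentage points.
- *Phase 1b patients dilute the table.* SAP 3 and 3.2 do group the lead-in with Phase 1b. But Protocol 9.4.1 limits the DLT summary to Phase 1a, and Protocol 4.1.3 and SAP 1.1.2 keep exploration patients out of the formal DLT calculations. The loose term Phase 1 in the set definition needs correcting, but it does not show that pooling is intended.
- *The DLT line in SAP 7.1.6 creates another denominator.* SAP 7 defaults to the Safety Analysis Set only where nothing else is specified, and 7.1.7 largely settles it.
- *A patient has already been lost.* Protocol 2.2.5.3 gives a minimum of one dose, but that range pools escalation with exploration and may include a patient still on treatment at the cutoff.

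**Conclusion.** The contradiction is real and should be corrected. As written, the plan removes only DLT-free patients from the reported DLT set, for want of a dose outside the one-cycle DLT assessment, although 4.1.2.3 counts them. With no replacement this can only raise a non-zero rate or leave it unchanged: 16.7% to 20.0% for one patient lost from a cohort reported at six with one DLT, and 10.0% to 11.1% or 12.5% for one or two lost from a cohort of ten.

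These figures are illustrations. They assume one DLT, no replacement, and at least one DLT-free patient who counts under 4.1.2.3 but fails the two-dose rule; how often that happens is unknown. With no escalation DLTs at the cutoff, a changed rate is mainly possible in the combination lead-in, whose results the documents do not give. Elsewhere only the denominator moves. The fault lies in reporting, not in dose selection.

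**What to change.** 1. Delete the two-dose condition from Protocol 9.2 and SAP 3.1.3, so that a DLT-free patient whose 21-day window is complete is not excluded for lack of a Cycle 2 dose.
2. Use one evaluability definition for dose decisions and for reporting. Before that, the sponsor must reconcile the synopsis, 4.1.2.3 and 7.3 on patients who leave the window early, including those who stop for a drug-related event that is not a DLT. Section 4.1.2.3 makes replacement optional for some early leavers. Section 7.3 makes it definite for unevaluable patients and refers to 4.1.2.2, which defines DLTs, not evaluability. The wording of 4.1.2.3 should not be copied as it stands, because it would admit one-dose patients whose window was not observed.
3. Replace Phase 1 in both definitions with Phase 1a dose escalation and combination safety lead-in, consistent with Protocol 9.4.1 and 4.1.3 and SAP 1.1.2.
4. As a separate matter, reconcile Protocol 6.4.5, which requires replacement of a lead-in patient counted as a DLT after a pembrolizumab dose modification, with 7.3, which replaces only unevaluable patients.

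No dose or replacement rule is proposed here. The cost is two rewritten definitions and a reconciliation of four protocol places (synopsis, 4.1.2.3, 6.4.5 and 7.3). No new data are needed. Protocol 9.3 already provides for describing and justifying changes to the final SAP in the study report.

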9.3 General Considerations

All analyses will be descriptive and will be presented by phase, dose group, cohort and overall as appropriate. In addition, all patients dosed at the MTD and/or RD will also be summarized as appropriate. Data collected in this study will be presented using summary tables and patient data listings. Continuous variables will be summarized using descriptive statistics, specifically the number of valid cases, arithmetic mean, median, standard deviation (SD), minimum, and maximum. Categorical variables will be summarized by frequencies and percentages.

A change to the data analysis methods described in the protocol will require a protocol amendment only if it alters a principal feature of the protocol. The SAP will be finalized prior to database lock. Any changes to the methods described in the final SAP will be described and justified in the clinical study report.

9.4 Statistical Analyses

9.4.1 Safety Analyses

Safety analyses will be performed separately within both phases of the study and for all patients combined. Data from all patients that receive any portion of at least one dose of FPA150 as monotherapy or one dose of FPA150 in combination with pembrolizumab will be included in the safety analyses. AEs, clinical laboratory information, vital signs, ECOG performance status, weight, ECGs, and concomitant medications/procedures will be tabulated and summarized. In addition, the incidence of DLTs in Phase 1a will be summarized.

Subject incidence of AEs will be summarized overall and with separate summaries for serious AEs, AEs leading to discontinuation, AEs leading to death, and NCI CTCAE Grade 3 or higher AEs. The patients' worst grade for each preferred term will be used for the summary of AEs by CTCAE grade. Treatment-related AEs and SAEs will also be summarized similarly.

Weight and vital signs will be summarized descriptively (N, mean, SD, median, minimum, and maximum). ECOG performance status will be summarized categorically and descriptively.

Shift tables displaying patient counts and percentages classified by baseline grade and maximum grade on treatment will be provided for laboratory data by cohort and overall as appropriate.

9.4.2 Efficacy Analyses

The ORR will be summarized with frequencies and percentages with 90% CI by each dose/cohort. The duration of response (DOR) for complete response (CR) and partial response (PR) patients and PFS for all treated patients will be summarized with descriptive statistics (N, arithmetic mean, SD, median, minimum, and maximum). The ORR, DOR, and PFS will

be determined using RECIST v1.1. Kaplan-Meier methodology will be used to estimate median DOR and PFS and corresponding 95% CI.

ORR, DOR, and PFS are defined below.

ORR: defined as the total number of patients with confirmed responses of either CR or PR per RECIST v1.1 divided by the total number of patients who are evaluable for a response.

DOR: defined as the time from onset of response (CR or PR) that is subsequently confirmed to the first observation of progressive disease or death due to any cause. Patients who are alive and progression-free at the time of data analysis will be censored at the time of their last assessment for tumor response.

PFS: defined as the time from the patient's first dose to the first observation of progressive disease or death due to any cause. Patients who are alive and progression-free at the time of data analysis will be censored at the time of their last assessment for tumor response.

More details of censoring rule for DOR and PFS will be outlined in SAP.

9.4.3 Pharmacokinetic Analyses

Individual and mean (\pm SD) serum FPA150 concentration-time data from monotherapy or in combination with pembrolizumab will be tabulated and plotted by dose level. Estimated individual and mean (\pm SD) PK parameters (eg, AUC, C_{\max} , C_{\min} , CL, $t_{1/2}$, V_{ss}) will be tabulated and summarized by dose level. Other descriptive statistics might be reported for serum FPA150 when appropriate and applicable.

For cohorts of FPA150 in combination with pembrolizumab samples for PK analysis will be collected and held at a central laboratory. Individual and mean (\pm SD) serum concentration-time data for FPA150 and pembrolizumab may be tabulated and plotted by dose level/cohort. Other parameters, such as dose proportionality, accumulation ratio, and attainment of steady state, may be evaluated, tabulated, and summarized by dose level/cohort if the data is available. The impact of immunogenicity on FPA150 exposure will be assessed, tabulated, and summarized by dose level as data allow.

9.4.4 Immunogenicity Analyses

A baseline ADA-positive subject is defined as a subject who has an ADA positive sample at baseline. An ADA-positive subject is a subject with at least one ADA-positive sample relative to baseline after initiation of the treatment. The frequency distribution of baseline ADA-positive subjects and ADA-positive subjects after initiation of the treatment will be summarized for FPA150 and pembrolizumab, respectively.

